12.10.1.2 Summary of Treatment Emergent Adverse Events by SOC and PT

Number and percentage of subjects and number of adverse events will be summarized by treatment, system organ class and preferred terms. Percentages will be based on safety analysis set. Events will be displayed in the descending order of frequency in “Total”.

The same will be repeated for treatment-emergent related AEs, treatment-emergent serious AEs, treatment-emergent related serious AEs. Serious AEs and Deaths will be listed separately for respective sections in CSR (as per ICH E3).

In DDP: Tables 14.3.1.2 to 14.3.1.8, Tables 14.3.2.1 and 14.3.2.2

12.10.1.3 Summary of Adverse Events by Relationship and Intensity

Number and percentage of subjects and number of events in each system organ class, preferred term and intensity (Grade 1-5) will be summarized by relationship for treatment-emergent adverse events and treatment. System organ class and preferred term will be displayed by descending order of frequency in “Total”. Intensity will be displayed in the alphabetical order.

In DDP: Table 14.3.1.9

12.10.2 Summary of Death

Number and percentage of deaths due to any cause, AE leading to Death by preferred term, Death due to COVID-19 (WHO score = 8) by visit will be summarized by treatment groups. Percentages are based on Safety analysis set.

In DDP: Table 14.3.2.3

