### **5.2.3. Exploratory Endpoints**

- Biomarkers
  - Changes in biomarkers and radiologic imaging over time with treatment
  - Relationship of baseline biomarkers to clinical outcomes

Note: All deaths on-study must include cause of death as per investigator assessment and relationship to study drug and/or COVID-19.

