## 11. STATISTICS

### 11.1. General Overview

All subjects given e 1 dose of study drug will be included in the Full Analysis Set (FAS) according to actual drug received; non-completers will be counted as failures in the primary efficacy analysis. Subjects receiving all 3 doses and evaluable for the primary Day 14 endpoint will constitute the per-protocol population for efficacy assessment. WHO severity score will be recorded daily while the subject is hospitalized, after discharge through Day 14, where feasible, and at each follow-up visit.

AE data will be summarized for the FAS by actual drug received using counts and proportions of subjects having an AE, each AE type, and an AE of each System Organ Class. SAEs and reasons for any early discontinuation will be summarized similarly. All deaths will be categorized by cause of death as per investigator assessment and relationship to study drug and/or COVID-19

Immunogenicity will be assessed on Days 1(predose), 28, and 90 days in all participants. Antibodies against pGSN will be assayed from frozen specimens to determine whether the investigational product induces an antibody response in recipients.

For Part 1, binary efficacy endpoints will be compared between treatments via stratified Cochran-Mantel-Haenszel (CMH) test and, to accommodate continuous covariates, via logistic regression. Continuous efficacy and biochemical endpoints will be compared between treatments via mixed model repeated measures analysis or analysis of covariance, depending on whether repeated measures are available or not. Time-to-event analysis via stratified log rank test and Cox proportional hazards model may also be carried out as supplemental analyses.

For Part 1, exploratory analyses looking at biomarkers and outcomes in each treatment arm will be conducted. Other exploratory analysis to compare the efficacy endpoint data from the rhu-pGSN group from this study to that of external control data may be carried out if appropriate. Sample size may be increased to improve the precision of the estimates of between-treatment comparisons if appropriate and if drug supplies are available.

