11.3.3 Visit Imputation

For assessments where shift summaries are required (WHO Severity Score and CURB-65 Score), records will be imputed for all subjects in Safety Analysis Set in all scheduled visits and marked as ‘Missing / Not Done’ if either the subjects did not attend the visit or discontinued or had missing assessment at the respective visit.

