11.5 Discontinued Subjects

Discontinued subjects will have safety assessments taken at Early Withdrawal visits. These will be presented separately and will not be combined with EOS if results are available.

The reason for discontinuation from the study will be mapped in the analysis as follows:

Primary reason for early discontinuation (As in CRF)	Reason for early termination from the study
Subject withdrew consent	Subject withdrew consent
Unacceptable AE	Unacceptable AE
Pregnancy	Pregnancy
Subject is unwilling or unable to continue the study or is lost to follow up	Subject unwilling / lost to follow-up
Subject is non-compliant with study procedures/study protocol	Protocol Deviation
Investigator decides that withdrawal from the study is in the best interest of the subject	At the discretion of the Investigator
Any clinically significant change in subject's medical condition (at the discretion of the Investigator)	At the discretion of the Investigator due to change in medical condition
Treatment unblinded	Treatment Unblinded
Sponsor decision to end the study	Sponsor decision to end the study
Death	Death
Other	Other

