12.9.2.2.4 Listing

Death Details will be listed by subject.

In DDP: Listing 16.2.7.4

12.9.2.3 Proportion of Subjects Alive on Days 7, 14, 28, 60 and 90

Number and percentage of subjects alive on Days 7, 14, 28, 60 and 90 without the following will be summarized. Percentages will be based on FAS. Subjects who discontinued from the study early or whose survival status is inconclusive on respective day will be considered as failure (Not Alive).

- Ongoing use of vasopressors
- Ongoing intubation/mechanical ventilation
- Ongoing residence in an ICU
- New ongoing need for dialysis/renal replacement therapy (RRT)

The analyses described in Section 12.9.1.1 will be repeated for each day as part of secondary analyses.

In DDP: Tables 14.2.4.1 and 14.2.4.2, Listing 16.2.6.2, 16.2.6.3, 16.2.6.4

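### The SAP's row for deaths due to COVID-19 is defined by WHO score 8, which carries no cause, so it can misattribute deaths and departs from the protocol's rule for classifying them

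*SAP*

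**What the plan says.** SAP 12.10.2 (Summary of Death) describes one table, by treatment group, on the Safety Analysis Set. It begins with "Number and percentage of deaths due to any cause, AE leading to Death by preferred term" and ends with the item at issue: "Death due to COVID-19 (WHO score = 8) by visit will be summarized by treatment groups". SAP 11.16.4 and Protocol 6.1 both give level 8 of the WHO scale as death, with no qualifier.

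The protocol treats cause of death as a separate item of data. Protocol 5.2.3 states: "All deaths on-study must include cause of death as per investigator assessment and relationship to study drug and/or COVID-19". Protocol 11.1 then makes this an analysis commitment: "All deaths will be categorized by cause of death as per investigator assessment and relationship to study drug and/or COVID-19". The synopsis repeats both.

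The SAP's other output specific to deaths is a listing, described in 12.9.2.2.4 only as "Death Details will be listed by subject". Section 12.10.1.2 also promises a separate listing of deaths. Section 13 (Changes to Planned Analyses) records two departures from the protocol, on daily WHO scores and on external controls. It does not mention the classification of deaths.

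**The concern.** The row's label claims a cause, but the code that defines it records only that the subject died. As written, a death that the investigator attributes to an unrelated event or to study drug would count as a COVID-19 death once it is scored 8. The classification that the protocol promised is replaced by a level of a severity scale, and the SAP does not say so.

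Attribution of deaths matters in this trial. The incidence of serious adverse events is a primary endpoint. In the earlier ICU study described in Protocol 4.4.2, 7 of 21 treated patients died and none of the 7 placebo patients did. The protocol's account of that result relies on the deaths having been judged unrelated to treatment and on baseline imbalance. Deaths from other causes are plausible here, since subjects with superinfection are eligible and follow-up runs to Day 90. A reader of the clinical study report could see a COVID-19 death count that disagrees with the fatal adverse events listed in the same table.

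**Working it through.** The plan gives no figure to reproduce. The check compares definitions.

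**1. What the row counts.** The row in SAP 12.10.2 is the set of subjects with WHO score 8. By SAP 11.16.4 and Protocol 6.1, score 8 means death. Hence:

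row count = recorded COVID-19 deaths scored 8 + recorded deaths from other causes scored 8.

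The label is correct only if the second term is zero.

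**2. Size of a possible overcount.** The documents give no expected split of deaths by cause, so the second term can be anything from 0 to all deaths scored 8. With the planned 30 subjects per arm in Part 1 (Protocol 7.1), one misattributed death moves an arm's percentage by 1/30 = 3.3 percentage points. That figure shows the scale of a single error. It says nothing about how likely one is.

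**3. Possible undercount.** The row is built by visit from WHO scores.
- Under SAP 11.3.3, records filled in for the shift summaries are "marked as ‘Missing / Not Done’ if either the subjects did not attend the visit or discontinued", and SAP 11.5 includes death among the reasons for early discontinuation.
- After discharge, daily scores through Day 14 are collected only where feasible (Protocol 9.1.1).
- SAP 8.1 keeps unscheduled visit data out of summaries.
- No rule assigns score 8 at the next scheduled visit after a death, or carries it forward.

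A death between scheduled visits may therefore never appear as a score of 8 in a by-visit table.

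**4. What the SAP tabulates elsewhere.**
- *Deaths from any cause:* the first item of the same table.
- *Reported cause:* fatal adverse events by preferred term, also in that table. Protocol 10.2 has the event that led to death reported as the SAE term, so this row works as a table of reported causes.
- *Relationship to study drug:* related serious events in SAP 12.10.1.1 and 12.10.1.2, and events by relationship and by Grades 1 to 5 in 12.10.1.3. Protocol 10.4 makes Grade 5 a fatal event.
- *Relationship to COVID-19:* no table.
- *Deaths (one per subject) by relationship to study drug:* no table. The outputs above count events and subjects with events. A subject with two fatal events could appear under two preferred terms.

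**5. Comparison with the protocol.** Protocol 11.1 requires deaths to be classified by cause and by relationship to study drug and/or COVID-19. The SAP covers cause through preferred terms and covers drug relationship at event level. It does not classify deaths by relationship to COVID-19, and it has no death-level table by relationship to study drug.

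**The case against.** The strongest reply is that this is loose wording with little consequence. Mortality endpoints are all-cause, the primary efficacy endpoint uses survival status and organ support, and the row has no test or decision rule attached. The all-cause count and the fatal events by preferred term stand in the same table, so a fatal pulmonary embolism, for example, would be visible by arm. All of this stands, and it sets the weight of the point.

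A second reply is that the authors may have meant a subset: COVID-19 deaths that also carry score 8. The scale grades COVID-19 illness, and placing the row beside all-cause deaths suggests a narrower count. That reading is possible, but the SAP names no cause variable that would produce the subset. If it was intended, the text still needs to name one.

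A third reply is that the Data Display Plan, which holds the table shells, is not among the documents, and that the content of the death listing is not described. Investigator attribution may appear there. A listing would still not be the classification by category that Protocol 11.1 describes, and it would not correct the label in SAP 12.10.2.

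A reader might go further and infer that the SAP reports neither cause of death nor relationship to study drug, and so hides a safety signal. The documents do not support this: preferred terms of fatal events and the relationship tables carry that information. A reader might also infer that the COVID-19 count must always equal the all-cause count. That is not established either, because the row depends on WHO scores recorded at visits and no rule guarantees a score of 8 for every death.

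**Conclusion.** The row is wrong as specified: a cause-specific label rests on a code without a cause, and the protocol's own classification of deaths is only partly carried out, with no entry in SAP Section 13. The consequence is modest. Deaths from other causes would be misattributed in one descriptive row while remaining visible in other tables. What is missing is a classification of deaths by relationship to COVID-19 and a death-level table by relationship to study drug.

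The row may be too high (by 0 up to all deaths scored 8) or too low (where no score 8 is recorded at a visit). Which of these occurs, if either, depends on data that the documents do not give. If every death were due to COVID-19 and scored at a visit, the row would be right, though not because of its definition.

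The conclusion rests on one inference: that the unqualified word for level 8 covers death from any cause. Nothing in either document restricts it.

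**What to change.** In SAP 12.10.2:

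1. Derive death due to COVID-19 from the investigator-assessed cause and relationship fields, and name those variables.
2. Tabulate deaths by arm, one per subject, by relationship to COVID-19 and by relationship to study drug, with a category for other or unknown.
3. If a row based on the WHO scale is kept, label it 'Death (WHO score 8), any cause' and state how score 8 is assigned at visits after the date of death.

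If the sponsor prefers not to present the protocol's classification, Section 13 should say so and give the reason.

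The cost is a few lines of SAP text and a revision of one descriptive table (14.3.2.3). The protocol already requires the data for every death. No endpoint, test or sample size is affected.

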12.10.3 Laboratory Assessments

12.10.3.1 Continuous Summary

Descriptive summary of absolute result and change from baseline in laboratory data will be presented by parameter and visit for safety analysis set. Each category (Hematology, Clinical Chemistry and Coagulation) will be represented in separate tables. Note that Laboratory assessments will be done only if required by SOC.

In DDP: Tables 14.3.4.1, 14.3.4.2, and 14.3.4.3

12.10.3.2 Categorical Summary

Number and percentage of subjects reporting laboratory interpretations (Normal, Abnormal Not CS and Abnormal CS, Not Done, Not required as per SOC) will be summarized by treatment, parameter, and visit. Each category (hematology, clinical chemistry, and coagulation) will be represented in separate tables. Percentages will be based on number of subjects with non-missing results in each visit within safety analysis set.

In DDP: Tables 14.3.4.4, 14.3.4.5 and 14.3.4.6

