### 7.2. Subject Inclusion Criteria

To be considered eligible to participate in this study, a subject must meet all the inclusion criteria listed below:

1. Hospitalized with laboratory-confirmed (RT-PCR+) or highly suspected (compatible with at least bilobar lung involvement without another plausible diagnosis) COVID-19
2. Age ≥ 18 years
3. **Part 1 only:** Weight ≥ 100 kg
4. **Part 1 only:** Within 24 hours of reaching a WHO severity score of 4-6 either:
  - a) At admission
  - b) While already hospitalized.
5. **Part 2 only:** Within 24 hours of intubation without ECMO with a WHO severity score of 6 or 7)
6. Informed consent obtained from subject/next of kin/legal proxy
7. Primary admitting diagnosis of pneumonia supported by a compatible clinical presentation with a documented infiltrate consistent with pneumonia on CXR or CT, as assessed by the admitting emergency department (ED), clinic, or ward physician or equivalent caregiver
  - Recommended (not mandatory) guidance/discretionary criteria defining patients with pneumonia satisfying all 4 categories below:
    - At least 2 symptoms: difficulty breathing, cough, production of purulent sputum, or chest pain
    - At least 2 vital sign abnormalities: fever, tachycardia, or tachypnea (thresholds -- fever: body temperature >100.4°F [38°C]; heart rate >100 beats/min; respiratory rate >24/min)
    - At least one finding of other clinical signs and laboratory abnormalities: hypoxemia (O2 saturation <90%), clinical evidence of pulmonary consolidation, or leukocytosis ≥ 1.5x10^4 or leukopenia <4x10^3
    - Chest imaging or CT chest showing at least bilobar pulmonary infiltrates
      - Principal Investigator (PI) to note radiologic findings in the eCRF
      - Radiology report and conclusion should be summarized in the eCRF

- A copy of the radiograph attached to be saved for review, if possible
- 8. A hyperinflammatory status (defined by increased ferritin ≥ 500 µg/L, D-dimer ≥ 1000 ng/mL, or CRP ≥ 75 mg/L)
- 9. During the course of the study starting at screening and for at least 6 months after their final study treatment:
  - a) Female subjects of childbearing potential must agree to use 2 medically accepted birth control methods
  - b) Male subjects with a partner who might become pregnant must agree to use reliable forms of contraception (i.e., vasectomy, abstinence), or an acceptable method of birth control must be used by the partner

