## **10.6. Laboratory Abnormalities**

To the extent possible, all laboratory abnormalities observed during the course of the study will be included under a reported AE term describing a clinical syndrome (e.g., elevated BUN and creatinine in the setting of an AE of "renal failure"). In these cases (e.g., an AE of renal failure), the laboratory abnormality itself (e.g., elevated creatinine) does not need to be recorded as an AE.

If a laboratory abnormality cannot be reported as a clinical syndrome, AND if the laboratory abnormality results in a therapeutic intervention (i.e., concomitant medication or therapy), is a dose-limiting toxicity, or is judged by the Investigator to be of other clinical relevance, then the laboratory abnormality should be reported as an AE.

Subjects experiencing AEs or clinically significant laboratory abnormalities will be assessed and appropriate evaluations performed until all parameters have returned to baseline levels or are consistent with the subject's then-current physical condition.

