7.2 Secondary Endpoints

7.2.1 Safety and tolerability

- *Incidence, causality, and severity of AEs (graded according to the National Cancer Institute [NCI] Common Terminology Criteria for Adverse Events [CTCAE] version 5.0) in rhu-pGSN vs placebo groups*
- *Frequencies of new or worsening clinically significant laboratory abnormalities in rhu-pGSN vs placebo groups*
- *Mortality rate irrespective of cause at Days 28 and 90*

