8.1 General Conventions

All analyses will be done using SAS (version 9.4, SAS Institute Inc., Cary, NC, USA).

Efficacy and Safety endpoints will be analyzed in a descriptive manner. Continuous data will be reported using the following descriptive statistics:

1. Number of observations (n)
2. Mean and Standard deviation (SD)
3. Interquartile Range (IQR)
4. Minimum (min) and Maximum (max)
5. Median

In addition:

6. Geometric mean & Standard deviation
7. Coefficient of variation (CV%)
8. Geometric CV%

will be reported for plasma concentration data and PK parameters. Categorical data will be presented using frequency (n = number of subjects; m = number of events) and percentage (%).

Listings will be provided for all data recorded in eCRF to study subject profiles. All listings will be sorted by treatment, subject ID, and date (if applicable). Unscheduled visit data will only be listed and not included in summaries.

All p-values will be displayed to four decimal places, with p-values less than 0.0001 presented as '<0.0001' and p-values greater than 0.9999 presented as '>0.9999'. Minimum and maximum values will be reported in the units of collection with 3 decimals being maximum value; the mean will be presented with 1 decimal place more and the standard deviation 2 decimal places more than the units of collection. Percentages for categorical summaries will be represented to 1 decimal place.

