12.10.3.3 Listings

All laboratory results will be listed for all subjects by visit and parameter. Out of range results will be highlighted.

In DDP: Listings 16.2.8.1, 16.2.8.2 and 16.2.8.3

Subjects with clinically significant laboratory results and subjects with out-of-range results will be separately listed by category, visit and parameter.

In DDP: Listings 16.2.8.4, Table 14.3.4.7

HIV and Pregnancy tests will only be listed by subject.

In DDP: Listing 16.2.8.5 and 16.2.8.6

Parameters collected in each laboratory category are listed below. In summaries and listings, parameters will be sorted in the order as below:

Category	Parameters
Hematology	Hemoglobin, Hematocrit, RBC, WBC, Platelet Count, Neutrophils, Lymphocytes, Monocytes, Eosinophils, Basophils, Reticulocyte Count,
Clinical Chemistry	Albumin, Alkaline Phosphatase, Alanine Aminotransferase (ALT), Aspartate Aminotransferase (AST), Bicarbonate, Direct Bilirubin, Total Bilirubin, Blood Urea Nitrogen, Lactate Dehydrogenase (LDH), Chloride, Creatine Phosphokinase (CPK), Creatinine, Amylase, Lipase, Potassium, Total Protein, Sodium, Ferritin, D-dimer, CRP, Procalcitonin, Urea, Total cholesterol (TC), HDL-C, LDL-C, Triglycerides
Coagulation	PT, PTT, aPTT, International Normalized Ratio (INR)

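### The by-visit laboratory table in SAP 12.10.3.2 gives prevalence, not the secondary safety endpoint of clinically significant abnormalities that are new or worse since baseline

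*SAP*

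**What the plan says.** - **Endpoint.** SAP 7.2.1, repeating Protocol 5.2.2: "Frequencies of new or worsening clinically significant laboratory abnormalities in rhu-pGSN vs placebo groups".
- **Planned table.** SAP 12.10.3.2: "Number and percentage of subjects reporting laboratory interpretations (Normal, Abnormal Not CS and Abnormal CS, Not Done, Not required as per SOC". These counts "will be summarized by treatment, parameter, and visit", and the percentage base is the subjects with a result at that visit.
- **Shift summaries.** SAP 11.3.3 names two scales: "For assessments where shift summaries are required (WHO Severity Score and CURB-65 Score". Laboratory data are not among them.
- **Unscheduled results.** SAP 8.1: "Unscheduled visit data will only be listed and not included in summaries". SAP 11.3.4 makes one exception: a repeat of a scheduled assessment is mapped back to its visit.
- **Entry condition.** Protocol 7.2, criterion 8: "A hyperinflammatory status (defined by increased ferritin", or by D-dimer or CRP above a threshold. The clinical chemistry panel in SAP 12.10.3.3 includes "Ferritin, D-dimer, CRP, Procalcitonin".
- **Summary of analyses.** SAP 16.1 assigns clinically significant laboratory results to descriptive summaries and says no more.

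Neither document defines new or worsening for a laboratory result.

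**The concern.** New and worsening both compare a subject with that subject's own earlier state. A table of how many subjects are abnormal at Day 7 cannot separate someone who was abnormal on arrival from someone who became abnormal after dosing. If three subjects resolve and three others become abnormal, the percentage does not move. The three categories also cannot show worsening in a subject who is already Abnormal CS at baseline.

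This matters because Protocol 4.7.1 puts the prior safety database at only 24 recipients of the drug, so laboratory safety is one of the main things this trial can add. The plan would report a different quantity under the endpoint's name. For some parameters, that quantity is less sensitive to a difference between arms.

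**Working it through.** The plan states no rate, power or sample size for this endpoint, so there is no figure to reproduce. The check has four steps.

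**1. What the endpoint needs and what the plan supplies**

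| Needed | Planned |
|---|---|
| Each subject's baseline CS status linked to later status | Separate counts at each visit; no laboratory shift table |
| Base: subjects who could have a new event | Base: subjects with a result at that visit |
| Any post-dose result | Scheduled results and mapped repeats |
| A rule for worsening | None |

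SAP 11.7 lets unscheduled results set the baseline. SAP 8.1 then leaves them out of the summaries after dosing.

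**2. How common entry abnormality is.** Criterion 8 is met by any one of three markers, so the three shares of subjects with a raised value sum to at least 100%. At least one marker is therefore raised in at least 1/3 of subjects. The documents do not say which marker, or how many raised values the investigator would call CS.

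**3. Which days the summaries can miss.** Haematology and metabolic-profile draws are scheduled on Days 1, 2, 3, 7 ± 1 and 14 ± 2 in the first two weeks (Protocol Table 5). The windows cover Days 1–3, 6–8 and 12–14. Days 4, 5, 9, 10 and 11 lie outside every window: 5 of 14 days. Protocol 6.1 expects laboratory tests during the hospital stay as standard of care indicates, so results on those days are likely.

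**4. Dilution within one parameter (illustration).** Assumptions, none from the documents except 30 per arm (Part 1):
- b = share CS at baseline
- r = 0.8 of these still CS at the visit
- i = new CS among those not CS at baseline: 10% placebo, 30% drug (true ratio 3.0)
- u = share of new events seen only at unscheduled draws

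Expected number Abnormal CS at a visit = 30 × [b·r + (1 − b)·i·(1 − u)].

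At b = 0.6 and u = 0:
- placebo: 30 × (0.48 + 0.04) = 15.6
- drug: 30 × (0.48 + 0.12) = 18.0
- ratio: 18.0/15.6 = 1.15

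In each arm, 30 × 0.48 = 14.4 of those counted are carry-over.

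| b | Placebo vs drug, u = 0 | Ratio | Placebo vs drug, u = 0.5 | Ratio |
|---|---|---|---|---|
| 0 | 3.0 vs 9.0 | 3.0 | 1.5 vs 4.5 | 3.0 |
| 0.3 | 9.3 vs 13.5 | 1.45 | 8.25 vs 10.35 | 1.25 |
| 0.6 | 15.6 vs 18.0 | 1.15 | 15.0 vs 16.2 | 1.08 |
| 0.9 | 21.9 vs 22.5 | 1.03 | 21.75 vs 22.05 | 1.01 |

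A count of new CS among subjects not CS at baseline, using all results, gives 3.0 in every row. At b = 0.6 and u = 0 the excess in number of subjects is unchanged: 18.0 − 15.6 = 2.4, and among true new cases 3.6 − 1.2 = 2.4. It is simply set against 15.6 placebo subjects instead of 1.2. With u = 0.5 the excess itself halves: 16.2 − 15.0 = 1.2.

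**The case against.** The strongest reply is that adverse event reporting already delivers the endpoint. Protocol 9.2.6 asks sites to report as AEs laboratory results that the investigator judges clinically significant. SAP 11.12 counts an AE as treatment-emergent if it starts or worsens after first dosing. SAP 12.10.1.2 tabulates these by arm with subject counts, whatever day they occur.

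Much of this stands. A reader might infer that a significant creatinine or ALT on Day 5 or Day 10, resolved by the next visit, would never be counted. The documents do not support that: both days fall inside the all-AE recording period, so the event should reach the AE tables. When a result belongs to a reported syndrome, Protocol 10.6 says that "the laboratory abnormality itself (e.g., elevated creatinine) does not need to be recorded as an AE", but the syndrome is still counted. A significant abnormality outside any syndrome is still to be reported.

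The AE route has three limits:
- Results folded into syndrome terms cannot be recovered by parameter.
- Non-serious AEs are recorded only through Day 14 (Table 5, footnote q; Protocol 10.7 says 14 days after the last dose), while haematology and chemistry visits run to Day 90.
- The SAP does not name the AE tables as this endpoint's analysis, and Protocol 5.2.2 lists AEs as a separate endpoint.

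Nor is baseline ignored altogether. SAP 12.10.3.1 summarises continuous change from baseline, and SAP 11.3 makes Baseline a summary visit, so arm-level percentages can be set side by side. Protocol 11.4.1 adds counts below, within and above the normal range. None of these gives the number of subjects with a new or worse CS result. SAP 12.10.3.3 also cites a Table 14.3.4.7 beside the listing of CS results. Its layout is in the Data Display Plan, which is not among the documents, but the SAP text gives it no rule for new or worsening.

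**Conclusion.** The point holds as a mismatch between a named secondary safety endpoint and the only stated frequency analysis of CS status. Following the SAP yields visit prevalence, with part of the endpoint recoverable from other tables. The primary efficacy analysis is untouched.

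The size differs by parameter. A reader might infer that the entry markers dilute every laboratory comparison. They do not: the table is by parameter, so raised ferritin, D-dimer or CRP affects only its own rows. For those rows, and any other parameter often CS at entry, the illustration shrinks a true ratio of 3.0 to between 1.45 and 1.03 as baseline CS prevalence goes from 30% to 90%, before any loss to unscheduled draws. For other parameters the weakness is the missing onset comparison and the exclusion of unscheduled results.

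These ratios rest on assumed onset, persistence and baseline shares, and on raised values being judged CS. They should not be read as a prediction. Visit prevalence among all subjects and onset among subjects at risk also have different denominators, so the two percentages should not be set against each other as if one replaced the other. Randomisation makes carry-over similar between arms in expectation, so the main effect is dilution, with chance imbalance possible at about 30 per arm.

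**What to change.** In SAP 12.10.3.2, and with a matching shell in the Data Display Plan, add for each parameter and arm:

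1. A shift table from the SAP 11.7 baseline interpretation to the worst interpretation after the first dose. Include unscheduled results by an explicit exemption from SAP 8.1.
2. **New:** number and percentage of subjects with baseline Normal or Abnormal Not CS and any later Abnormal CS. The denominator is subjects with such a baseline and at least one post-dose result.
3. **Worsening:** among subjects Abnormal CS at baseline, a pre-stated rule, for example a higher CTCAE v5.0 grade derived from the result where a grade exists, and otherwise a value further from the reference range in the same direction.

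Name this table as the analysis of the endpoint in SAP 16.1, and keep the by-visit table as a supplement.

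The cost is SAP wording and one table, with no new data collection. There are two downsides. Sicker subjects have more unscheduled draws and so more chances to be counted. Grades must also be derived from local-laboratory values, because Protocol 10.4 specifies CTCAE grading for AEs only. To handle the first, report the number of subjects and tests per arm and show the table with and without unscheduled results.
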